3.1.4 Safety Population

This study records safety events for all participants that sign IC. Therefore, the safety population consists of all participants who sign IC.

3.1.5 Inducted Population

The inducted population consists of enrolled participants that receive the first XR-NTX while in the unit (i.e., all success for the primary outcome).

3.1.6 Provider/Staff Population

The provider/staff population includes providers and staff at the sites who complete the Organizational Readiness to Change (ORCA) survey (OR1/OR2), and/or the site-level Organization Level Clinical Implementation (OLC), and Fidelity to Implementation Checklist (FC1/FC2) assessments.

3.2 General Definitions

3.2.1 Induction Phase

The induction phase Day 1 is defined as the day of the admission (E97ADMDT) as recorded on the ENRC or ENRD forms. The induction phase for enrolled participants begins with day of admission (induction phase Day 1) and ends on the day of XR-NTX receipt or day of failure of the induction protocol. The maximum length of the induction phase is 30 days (Day 1 – Day 30). Note that the end of the induction phase does not always coincide with the participants being discharged from the unit.

3.2.2 Post-induction Phase

The post-induction phase Day 1 is defined as the day after receipt of the first XR-NTX injection (EOI.EOIINJDT) or the day after failing the induction protocol (EOI.EITERMDT). The planned length of the post-induction phase is 56 days (Week 1 – Week 8) with the upper window for the last post-induction visit set at Day 62 (Day 56 + 6-day window). For successful inductions (i.e., those that receive first XR-NTX while on the unit), study visits are planned at Week 1 (Day 6+/- 4 days), Week 2 (Day 14+/- 3 days), Week 3 (Day 21+/- 3 days), Week 4 (Day 28+/- 3 days), Week 6 (Day 42+/- 6 days), and Week 8 (Day 56 +/- 6 days). For induction failure (i.e., those that do not receive first XR-NTX while on the unit), study visits are planned at Week 4 (Day 28+/- 3 days), and Week 8 (Day 56 +/- 6 days).

3.2.3 Baseline Visit

The baseline visit is performed on day of enrollment in the study Segments C or D or after for all participants that sign the IC. The baseline dates may vary across different assessments.

3.2.4 Baseline Value

The baseline value will be defined as the assessment collected at the Baseline Visit or the first available record starting with the admission day.

3.2.5 Safety Window

The safety window for all participants enrolled in the study begins at day of signing the IC and ends at 30 days post last study visit.

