6.1.4 Training in SP and RP procedures

At the beginning of the trial all sites will receive training in the study procedures. In addition, the five sites chosen to offer SP will receive an overview training and review of practices in the SP, while the site selected to start with RP in Step 1 will receive an overview training in the RP. This didactic training will occur before the study start date. At the start date participant enrollment begins, the units chosen to begin by offering SP will receive academic detailing in SP, while the unit assigned to begin RP will receive the further targeted RP implementation facilitation intervention (training and academic detailing) in an 8-week pre-implementation or preparation phase before the start of the RP implementation step. Upon transition to RP implementation (or start of the step), RP academic detailing and coaching support will be held weekly or more frequently based on the site's needs. After individual site-level coaching support sessions, all sites randomized to RP will participate in collaborative coaching sessions that occur weekly or more frequently based on sites' needs.

Study Schema

The flow of a patient-participant through the study, at either SP or RP sites, will proceed in four phases (see Figure 1).

6.1.4.1 *Phase 1 & 2 Inpatient Induction (Recruitment and Induction Phase)*

The clinical procedures for all individuals interested in XR-NTX will be determined by the assignment of the unit to either the Rapid or Standard Procedures and the clinical judgement of the unit staff. These will begin immediately upon admission and will be independent of study participation. Recruitment for research participation will occur independent of the clinical procedures any time from seven days before admission until the fourth day of admission.

Research Recruitment

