10.1 Pre-screening, Consent and Screening (Phase 1)

Participants will be recruited from the population of individuals presenting for treatment of opioid use disorder at the participating study sites.

Pre-screening will be completed before participants are approached for informed consent. All patients admitted to the unit with an OUD diagnosis should be pre-screened for the study and entered on the Participant Pre-Screening Log as well as on the pre-screening enrollment form in Advantage eClinical. The following will be assessed at pre-screening: current and active OUD, demographics, eligibility to receive XR-NTX and willingness to participate in the study.

All participants who are interested may begin the informed consent procedures up to 7 calendar days prior to the inpatient admission or during the first four calendar days of admission. All participants must sign the informed consent and complete screening procedures prior to the fourth calendar day of admission to be eligible to enroll in the Rapid Procedure or Standard Procedure. The timing of consent and screening procedures is flexible, and allows sites to customize recruitment, consent, and screening procedures to accommodate local conditions. Obtaining consent and screening/baseline data early in the admission will allow a full accounting of persons interested in study enrollment. For individuals consenting after admission, data will be collected about medication administration starting from admission using medication flowsheets and EMR abstraction (performed and confirmed by study staff).

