10.1.1 Informed Consent Procedures for Participants

Candidates for the study are given a current IRB-approved copy of the Informed Consent Form to read. Appropriately qualified and trained study personnel explain all aspects of the study in lay language and answer all the study candidate's questions. Study procedures and the potential risks and benefits of participating in the trial will be explained. Staff will be available to answer questions about the consent form while participants are reviewing it.

Prior to signing the consent form, the participant must pass a brief consent quiz to illustrate comprehension of the study activities - understanding of the project, the purpose and procedures involved, and the voluntary nature of his/her participation. Those who cannot successfully answer quiz items have the study re-explained by research staff with a focus on aspects they did not understand. Those who demonstrate understanding of the study and voluntarily agree to participate are asked to sign the Informed Consent Form. After passing the quiz and signing the consent form, participants will be offered a copy of the forms to keep for their records. The informed consent process and quiz will take approximately 30-45 and 5 minutes to complete, respectively.

Given the multi-site nature of the trial, it is possible that ancillary studies, or long term follow up studies, will be proposed before or after the study begins recruitment. For this reason, during the informed consent process, we also will seek permission to contact the participant in the future

about other study opportunities.

Participants are not administered any study assessments or procedures prior to signing informed consent. The informed consent includes a HIPAA Authorization to permit study staff to access the participant's medical records at the study site relating to the inpatient admission; the purpose of this is to capture study related clinical information that is collected during routine treatment (daily vitals, daily COWS, medication administration log, etc.).

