22.5 Site's Role in Eliciting and Reporting Safety Events

Appropriately qualified and trained personnel will elicit participant reporting of TSEs and SAEs at each study visit designated to collect these events. TSEs (medical and/or psychiatric) assessment will initiate with participant consent and follow-up of ongoing events will continue through resolution or 30 days post last study visit. Study personnel will obtain as much information as possible about the reported TSE/SAE to complete the TSE/SAE forms and will consult with the Safety Monitor/Medical Monitor as warranted.

Standard reporting, within 7 days of the site becoming aware of the event, is required for reportable TSEs. Expedited reporting (within 24 hours of their occurrence and/or site's knowledge of the event) is required for reportable SAEs (including death and life-threatening events). Sites are responsible for reporting SAEs to the IRB of record, per the IRB or record's guidelines.

Sites are required to enter reportable TSEs and SAEs in the Advantage eClinical system. The TSE form is used to capture reportable TSEs. The AE/SAE form set is used to capture SAEs (as defined in the protocol). In this protocol, only SAEs are being reported on the AE/SAE form set. Additional information may need to be gathered to evaluate SAEs and to complete the appropriate CRFs and the summary. This process may include obtaining hospital discharge reports, medical records, autopsy records or any other type records or information necessary to provide a complete and clear picture of the serious event and events preceding and following the event. If the SAE is not resolved or stable at the time of the initial report or if new information becomes available after the initial report, follow-up information must be submitted as soon as possible.

Any serious adverse reactions will be followed until resolution or stabilization for as long as possible beyond the end of the study. If the study team is unable to follow up with individuals with reportable safety events, every effort will be made to connect these individuals with the appropriate community-based treatment.

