2.2.2 Study Assessments

All assessments and corresponding case report forms by study phase and study visit are described below.

During pre-screening (Day -7 up to Day 3 of admission), potential participants will be assessed for basic eligibility to move forward in the study. Patients that meet pre-screening basic eligibility criteria will be asked to sign the informed consent (IC) no later than Day 4 of admission. Patients that sign the IC enter the screening phase and are assessed for eligibility to enroll in the study no later than Day 4 of admission. The following assessments are performed during screening: Demographics (DEM), Prisoner Status Assessment (PSA), Locator Information Form (LIF), Concomitant Medications (CMX), Medical Psychiatric History (MHX), DSM-5 Checklist (DSM), Pregnancy and Birth Control Assessment (PBC), and Urine Drug Screen (UDS).

Following the final confirmation of eligibility for study enrollment participants complete baseline assessments during Days 1-4: Study Demographics (D97), Genetics (GEN), Family Origin (FAM), Alcohol and Substance use (ASU), Non-Medical and other Services (NMS/NM2), Timeline Follow-back – Substance and MOUD (TAP/T97/M97), Concomitant Medications (CMX), Pregnancy and Birth Control Assessment (PBC), Urine Drug Screen (UDS), Daily Medication Administration Log (DMA), Clinical Opiate Withdrawal Scale (COW), and Medical Management (MGT). In addition, the following self-reported baseline assessments will be collected from participants: Additional Demographics (S97), Opioid Craving Scale Inpatient (OCI), Overdose Questionnaire (ODQ), The Subjective Opioid Withdrawal Scale (SBW), Cannabis Use Assessment (MJA), Tobacco Use History (TUH), Fagerström Test for Nicotine Dependence (FND), Motivation Scale (MTV), Quality of Life (QLP), PROMIS (PRO), Panic Disorder Assessment (PDA), Generalized Anxiety Disorder (GA7), PTSD Checklist for DSM-5 (PCL), Patient Health Questionnaire-9 (PHQ), Mental Health Assessment (MHA), Adult ADHD Self-Report Screening Scale for DSM-5 (AAS), Self-Report of Hepatitis Testing and Treatment (HEP), Self-Report of HIV Testing (HIV) and COVID-19 Impact Assessment (CVD).

Induction Phase Assessments (Day 1 – Day 30)

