The induction phase for enrolled participants (within both RP and SP) begins with day of admission (induction phase Day 1) and ends on the day of XR-NTX receipt or day of failure of the induction protocol. The maximum length of the induction phase is 30 days. For participants who leave the unit prior to Day 30, the date of leaving the unit without a medication would be equivalent to date of failure as recorded on the EOI form per the CRF manual. Daily and weekly assessments will be conducted during the induction phase as follows:

- Daily assessments (DMA, Low Dose Naltrexone Titration [LDN] for the Rapid Protocol only, COW, OCI, SBW, Psychosocial and Medical Treatment Participation log [PST]).

- Weekly assessments (GA7, PHQ).
- Assessments collected prior to first XR-NTX injection include UDS (all participants) and PBC (females only).
- Data will be collected retrospectively starting with induction phase Day 1, using medication flowsheets and EMR abstraction (performed and confirmed by study staff). The following assessments may be retrospectively collected/abstracted: DMA, COW, UDS and PBC.
- End of Induction (EOI) and End of Induction Survey (EIP) are collected at the end of the induction phase regardless of whether the participant receives their first dose of XR-NTX on the unit, if the participant terminates the induction protocol early, or if they exceed the maximum window allowed for the induction phase.

Post-Induction Phase Assessments (Week 1 – Week 8)

The post-induction phase will begin the day after receiving XR-NTX injection or the day after failure of the induction protocol (Day 1 post-induction). During the 8-week post-induction phase, participants will receive medication management visits per the site's standard clinical practice, plus an additional two XR-NTX injections, expected at four and eight weeks after the first XR-NTX injection, along with other psychosocial treatment as per the standard of care provided by each site. The following assessments will be conducted during post-induction phase at Weeks 1, 2, 3, 4, 6 and 8: Missed Visit and Visit Documentation (V97), TAP/T97/M97, MGT, OCO, ODQ, SBW, OES, GA7, PHQ, PST. UDS (all participants) and PBC (females only) will be assessed prior to each XR-NTX injection. Additional assessments will be performed at week 3 (PSA) and week 4 and 8 (INN, NMS/NM2).

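### Safety recording starts at consent but treatment and induction Day 1 start at admission, so up to 3 induction days of late consenters are tabulated as observed when TSE/SAE recording was not required

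*SAP*

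**What the plan says.** **Start of safety recording.** SAP 3.2.5: "The safety window for all participants enrolled in the study begins at day of signing the IC". Protocol 22.5 agrees: "TSEs (medical and/or psychiatric) assessment will initiate with participant consent".

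**Start of treatment.** Protocol 6.1.4.1 says of the clinical procedures for the site's assigned regimen: "These will begin immediately upon admission and will be independent of study participation". Protocol 10.2 confirms that treatment over the first four days follows whichever procedure the site is then offering. SAP 3.2.1 makes the day of admission induction Day 1.

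**Latest consent.** Protocol 10.1 lets consent begin "up to 7 calendar days prior to the inpatient admission or during the first four calendar days of admission". SAP 2.2.2 has patients "sign the informed consent (IC) no later than Day 4 of admission". Protocol 10.1 also requires consent and screening to be finished before the fourth calendar day, which does not match the SAP's limit.

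**What is recovered for the days before consent.** SAP 2.2.2: "The following assessments may be retrospectively collected/abstracted: DMA, COW, UDS and PBC" (medication log, COWS, urine drug screen, pregnancy test). Protocol 12.2.2 adds SOWS. Neither document lists TSE or SAE forms.

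**How the data are used.** Safety during the induction phase is a key secondary outcome (SAP 8.4), with equivalent TSE and SAE rates hypothesised (SAP Table 5). SAP 10.1 tabulates TSEs by procedure and phase and compares them with Fisher's exact test. The percentages of participants with a TSE in the Table 52 shell use all enrolled participants as denominator.

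**The concern.** Opening safety recording at consent is usually sound because treatment follows consent. Here treatment can come first. For anyone who consents after the day of admission, the induction phase used for analysis begins before the period in which TSEs and SAEs must be recorded. The plan recognises the same gap for other data and closes it by chart abstraction, but not for safety events.

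The Table 52 Induction rows give no sign of this. Every enrolled participant is counted as if followed from Day 1, and an event on an uncovered day is not distinguished from no event. The days at issue matter clinically: under protocol Table 6B, RP Days 2 and 3 carry standing clonidine and clonazepam, and Day 3 the first oral naltrexone. Protocol 4.1.2 names both more severe precipitated withdrawal and side effects of standing adjunctive medication as risks of the rapid method. Falls, acute mental-status change and precipitated withdrawal are all TSEs (SAP 3.2.6).

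**Working it through.** **1. Planned induction length.** Protocol 16.1.2 puts the end of induction at about Day 6 (RP) and Day 13 (SP). The regimen components reproduce this:
- RP (protocol 10.4.3): 1 day buprenorphine + 1 washout + 4 naltrexone = 6.
- SP (protocol 6.1.4.1): 5-day taper + 8-day washout = 13.

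**2. Uncovered share.** The window includes the day of signing, so consent on Day d leaves d − 1 days uncovered. Share = (d − 1)/6 for RP and (d − 1)/13 for SP, assuming buprenorphine starts on the day of admission.

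| Consent day | RP | SP |
|---|---|---|
| On or before Day 1 | 0% | 0% |
| Day 2 | 1/6 = 16.7% | 1/13 = 7.7% |
| Day 3 | 2/6 = 33.3% | 2/13 = 15.4% |
| Day 4 | 3/6 = 50.0% | 3/13 = 23.1% |

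For the same consent day in both arms the ratio is 13/6 = 2.17. Over the stated lengths (RP 5–7, SP 13–14 days) it runs from 13/7 = 1.86 to 14/5 = 2.80. If the protocol's deadline before the fourth day governs, the Day 3 row is the maximum.

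**3. Two clocks.** Consent day is counted from admission, but protocol 2.4 and 6.1.4.1 count the regimens from the first buprenorphine dose. Protocol 10.4.1 allows a wait before that dose, and SAP 6.0 tabulates pre-buprenorphine days. With an assumed lag of k days and consent on Day 4, the shares are 3/(6 + k) and 3/(13 + k):
- k = 1: 42.9% and 21.4%, ratio 2.00
- k = 2: 37.5% and 20.0%, ratio 1.88
- k = 3: 33.3% and 18.8%, ratio 1.78

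Regimen day is then admission day minus k, so on the planned schedule naltrexone falls on an uncovered day only if k = 0.

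**4. Unequal consent timing.** RP on Day 3 with SP on Day 4 gives (2/6)/(3/13) = 1.44. The reverse gives (3/6)/(2/13) = 3.25.

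**5. Whole safety window.** Adding 56 post-induction days and 30 follow-up days, consent on Day 4 leaves 3/92 = 3.3% (RP) and 3/99 = 3.0% (SP) uncovered. The imbalance is confined to the induction rows.

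**6. Direction.** The documents give no event rates. As an illustration, assume the same constant daily hazard h in both arms and consent by everyone on Day 4. Risk is 1 − exp(−h × days).

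| h | All days: RP, SP | Covered days: RP, SP |
|---|---|---|
| 0.005 | 0.030, 0.063 | 0.015, 0.049 |
| 0.01 | 0.058, 0.122 | 0.030, 0.095 |
| 0.02 | 0.113, 0.229 | 0.058, 0.181 |

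At h = 0.01 the RP:SP risk ratio moves from 0.058/0.122 = 0.48 to 0.030/0.095 = 0.32, away from equality. If RP events instead cluster on Days 2–3, RP is understated for a different reason. The direction depends on when events occur.

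**The case against.** A reader might infer that RP events are undercounted and the comparison pushed towards equivalence. The documents do not support that. Both arms lose the same maximum of 3 days, and Table 52 counts participants with an event, so what matters is how many events fall on those days. SP Days 1–3 also carry early withdrawal. At most the first of four naltrexone days is uncovered: 1 mg of the 15 mg tabulated for Days 3–6 (1 + 2 + 6 + 6). The later titration days, the injection and the adjunctive taper are all within the window. SAP 11.0 calls the key secondary outcomes non-confirmatory, and no equivalence margin is set for TSEs.

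A reader might also infer that early harm goes unrecorded altogether. That is too strong. COWS and SOWS are abstracted, the chart authorisation covers daily vitals (protocol 10.1.1), and the baseline overdose questionnaire asks about earlier overdoses. Hypotension is a TSE only with medical sequelae, and sedation is not itself listed.

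These points stand and limit the claim. They do not close the gap: abstracted COWS and SOWS do not feed Table 52 or the SAE tables, and do not capture falls or mental-status change.

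Finally, late consent may be rare. SAP 8.3 reports six participants enrolled more than 4 calendar days after admission under an older protocol version. That shows late entry occurred, but concerns enrolment, not consent.

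**Conclusion.** The mismatch is in the text and should be corrected. For participants who consent after the day of admission, up to 3 induction days fall outside required TSE/SAE recording, yet the Induction rows treat them as observed.

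The loss is zero for consent on or before Day 1, and the overall loss cannot be computed because the consent-day distribution is not given. The 50% versus 23% is a worst case for an individual participant: consent on Day 4, buprenorphine on the day of admission, and the same consent timing in both arms. It becomes 33% versus 15% if the protocol's earlier deadline governs. The ratio of about 2.2 falls to about 1.8 with a 3-day buprenorphine lag. Whether, and in which direction, the RP–SP comparison is biased is not established.

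**What to change.** - In SAP 3.2.5 and protocol 22.5, start the safety window for enrolled participants at the earlier of consent and admission.
- In SAP 2.2.2, add TSEs and SAEs to the items abstracted from the chart back to admission.
- Flag abstracted events, and show the Table 52 Induction rows and the SAE tables with and without them.
- Report consent day relative to admission by procedure. Consent and admission dates are both already captured (SAP 10.1 and 3.2.1).
- Reconcile the consent deadline in protocol 10.1 with that in SAP 2.2.2.

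Staff already abstract charts from admission, and the consent form's authorisation serves "to permit study staff to access the participant's medical records at the study site relating to the inpatient admission", so the mechanism exists. The costs are modest but not nil. Abstracted events may be less complete than elicited ones and need clinician review of severity and relatedness. They are seen only in patients who stayed to enrol, so someone who had an event and left stays uncounted. The SAP's Table 55 shell already carries counts for 415 participants, so the abstraction may have to be done retrospectively across six sites.

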3.2.6 Targeted Safety Event

The targeted safety events (TSEs) for this study are the events listed below and recorded on the Targeted Safety Event (TSE) form:

- Fall event (related to medical/psychiatric condition such as dizziness, confusion with head injury)
- Acute change in mental status (i.e., disorientation, amnesia, cerebrovascular accident, coma)
- Acute medical complication likely exacerbated by the stress of withdrawal (i.e., hypertensive crisis, hypotensive event with medical sequelae such as fall and/or requiring urgent fluid resuscitation, severe chest pain, acute respiratory decompensation, asthma attack, diabetic ketoacidosis, severe hypoglycemia, severe electrolyte abnormalities (hyper-/hyponatremia, hyper-/hypokalemia), precipitated withdrawal)
- Acute psychiatric symptoms (i.e., psychosis, hypomania, severe agitation, violence)

Other safety events will also be captured on study specific forms (for example, COWS, SOWS, PHQ-9, Medication Injection Site Abnormality Log and Overdose Questionnaire).

TSEs and other safety events captured on study specific forms will not also be reported as an AE unless the event meets the serious adverse event (SAE) definition.

